4.5. PRIOR AND CONCOMITANT THERAPIES

4.5.1. Definition

Previous therapies (products and/or procedures) are defined as therapies that have been stopped within 6 months preceding baseline visit and prior to the first investigational product application that may have an impact on inclusion/exclusion criteria should be recorded in the eCRF.

Concomitant therapies are defined as follows:

- any existing therapies ongoing at the time of the baseline visit (ongoing at the time of the first investigational product application), or
 - any changes to existing therapies (such as changes in dose or formulation) during the course of the clinical trial, or
- any new therapies received by the subject since the baseline visit (first investigational product application).

4.5.2. Categories

The following two categories will be considered for previous and concomitant therapies:

- Products/therapies including, but not limited to, prescription, over-the-counter (OTC), birth control pills/patches/hormonal devices, vitamins, moisturizers, sunscreens, herbal medicines/supplements, and homeopathic preparations.
- Medical and surgical procedures including, but not limited to, laser/radiation procedures, dermal fillers, X-rays, etc.

4.5.3. Recording

Previous and concomitant therapies will be recorded on the Drugs/Therapies Form (for drugs/therapies) and/or on the Medical and Surgical Procedures form (for medical/surgical procedures) in the electronic case report form (eCRF).

Concomitant therapies will be recorded, reviewed, and updated at each trial visit.

Any new concomitant therapy or modification of an existing therapy may be linked to an adverse event (AE). A corresponding Adverse Event Form must be completed to account for the change in therapy, except in some cases such as therapy used for prophylaxis, dose modification for a chronic condition, etc.

4.5.4. Authorized therapies during the clinical trial

Unless listed under the Exclusion Criteria above (see section 4.4, criteria 10 and 11) or in Prohibited Therapies (see section below 4.5.5), all therapies are authorized.

Subject must use the provided moisturizer and cleanser as required for the symptomatic relief of skin dryness or irritation (use of moisturizer with sunscreen and cleanser other than the provided ones must be recorded in the eCRF as concomitant therapy).

Oral vitamin A supplement (up to the recommended daily allowance) and plain penicillin are acceptable.

Systemic anti-inflammatory medication up to 21 days of treatment in total is also acceptable; however, it should be avoided for **1 week** prior to the final trial assessments.

Also subjects should be instructed to avoid excessive sun-exposure wind and cold. Cosmetics are to be used minimally and not at all during evaluation visit or photography of the skin.

4.5.5. Prohibited therapies during the clinical trial

The following drugs/procedures are prohibited because they may interfere with the efficacy/safety assessment of the investigational product, or because they may interact with the metabolism of the investigational product:

- All topical or systemic drugs/procedures listed in exclusion criteria (section 4.4, criteria 10 and 11),
- Any irritating topical products (medicated or abrasive soaps and cleansers, soaps and cosmetics that have strong skin-drying effect and products with high concentrations of alcohol, astringents, spices, or limes),
- Any other drugs/procedures which at the investigator's judgement are liable to interfere or interact with the efficacy and the safety of Epiduo[®] Forte / TactuPump[™] Forte[®] gel.

If prohibited therapies become a necessary treatment for the safety or best interest of the subject, GALDERMA R&D should be notified to discuss possible alternatives prior to administration of a prohibited therapy and to discuss the pertinence and the modalities for the subject to continue in the clinical trial.

4.5.6. Procedures / reasons for discontinuation

An Investigator may decide to discontinue a subject from the clinical trial for safety reasons.

Although the importance of completing the entire clinical trial should be explained to the subject by the clinical trial personnel, any subject is free to discontinue his/her participation in this clinical trial at any time and for whatever reason, specified or unspecified, and without prejudice.

Subjects who discontinue the clinical trial prematurely should be fully evaluated, whenever possible. The procedures corresponding to the next theoretical visit should be performed (e.g. if a subject discontinues **after** week 2, complete the week 8 visit procedures). Additional final procedures will be conducted for all premature discontinuation as indicated in the trial flow chart section 5.4. The appropriate eCRF pages should be completed.

For all subjects who prematurely discontinue the clinical trial, the reason must be carefully documented by the investigator on the Exit Form, and, if applicable, on the Adverse Event Form for discontinuation due to an AE.

A subject who has been enrolled and assigned a kit number cannot be replaced by another subject if he/she discontinues the clinical trial for any reason.

In the case of early termination, the investigator should ensure that the subject receives appropriate therapy for his/her condition.

The sponsor may also decide to prematurely terminate or suspend the clinical trial or the participation of a subject in the clinical trial.

All data gathered on the subject prior to termination will be made available to the sponsor.

Reasons for clinical trial completion/discontinuation, as listed on the Exit Form of the eCRF are described below:

Normal trial Completion	Subject completes the clinical trial as planned in the protocol
Pregnancy	Withdraw the subject from the clinical trial following the procedure described in the protocol section 8.2.3.1
Lack of efficacy	Investigator judgment only: based on therapeutic/disease-state expectations. If subject opinion only, mark "withdrawal by subject" and document it in the comment section of the eCRF Exit Form
Adverse Event	Complete eCRF Adverse Event Form
Withdrawal by subject	Includes consent withdrawal, subject relocation, schedule conflicts, etc... Does not include AE. . Explain the reason for withdrawal in the comments section of the eCRF Exit Form.
Protocol Violation	Explain the violation in the comments section of the eCRF Exit Form
Lost to Follow-up	Confirm with 2 documented phone calls and a certified letter (delivery receipt requested) without response. Explain in the comments section of the eCRF Exit Form.
Other	This category is to be used for a subject who discontinues for a reason other than those specified in the predefined categories above. Explain the reason for discontinuation in the comments section of eCRF Exit Form.

If reason for discontinuation is "withdrawal by subject" or "other", the subject must be questioned to rule out the possibility of an AE; this should be documented in the eCRF.

5. INVESTIGATIONAL PLAN

5.1. OVERALL CLINICAL TRIAL DESIGN

This clinical trial will be conducted as a multi-centre, open-label prospective trial involving subjects aged at least 12 years old inclusive with dark skin type phototype IV to VI from one of the 3 ethnic/race backgrounds: Asian, Latin American and Black/African-American with moderate to severe acne vulgaris on the face and meeting other specific eligibility criteria.

Approximately 60 subjects will be enrolled in 4 sites located in Mauritius, USA and Singapore. 20 subjects are planned from each site.

One third of subjects should have dark skin with **Asian** ethnic/race background:

One third of subjects should have dark skin with **Latin American** ethnic/race background:

One third of subjects should have dark skin with **Black/African-American** ethnic/race background:

In each ethnic/race backgrounds (Asian, Latin American and Black/African-American) approximately **one third** of subjects should have “Severe acne” (IGA 4) and **two third** “Moderate acne” severity (IGA 3).

All eligible subjects will receive Adapalene 0.3% - BPO 2.5% gel (Epiduo[®] Forte / TactuPump[™] Forte gel) once daily on the whole face.

There will be 5 trial visits: at baseline, week 2 (\pm 1 day), week 8 (\pm 3 days), week 12 (\pm 3 days), and week 16 (\pm 5 days).

5.2. DISCUSSION OF CLINICAL TRIAL DESIGN

This clinical trial will assess subject reported outcomes with a product marketed in USA under the name Epiduo[®] Forte gel and TactuPump[™] Forte gel in Canada, used according to its labeling information (indication, selected population, dose regimen). Therefore, this trial will be classified as Phase IV study in USA. Meanwhile, as this product is not marketed in Mauritius and Singapore (CTD recently submitted) therefore this trial is classified as a Phase IIIb trial for Mauritius and Singapore.

According to clinical studies performed with Epiduo[®] in acne, 3 months treatment is sufficient to treat acne. As this trial aims to treat moderate to severe acne consequently, treatment period is fixed to 4 months as a maximum in order to have a complete cure of acne.

Since acne is a chronic and long-lasting skin condition which could affect seriously the psychosocial development resulting in emotional problems it is deemed important to evaluate subjects' quality of life before and after treatment.

For this subjects will complete DLQI or cDLQI for children, at baseline, Week 12 and at last trial visit.

A satisfaction questionnaire on use of the investigational product will be completed by subjects at Week 12 and at end of the trial.

An acceptability questionnaire on use of the non –investigational products will also be completed by subjects at end of the trial.

This clinical trial should allow evaluation of subjects' reported outcome after use of the investigational product Adapalene 0.3% - BPO 2.5%.

5.3. CLINICAL TRIAL DURATION AND TERMINATION

The average planned period for the clinical trial from First Subject In (FSI) to Last Subject Out (LSO) is 11 months. The end date of the clinical trial will be the date of the last visit of the last subject who participates in the clinical trial.

The planned duration of recruitment (i.e. From FSI to Last Subject In (LSI)) is approximately 7 months.

The clinical trial may be terminated by the investigator at his/her clinical trial site at any time with appropriate notification to *GALDERMA R&D*. Likewise, *GALDERMA R&D* may terminate the clinical trial and/or the participation of the clinical trial site(s) with appropriate notification.

The expected duration of subject participation is 16 weeks.

5.4. CLINICAL TRIAL FLOW CHART

PROCEDURES	CLINICAL TRIAL VISITS				
	Visit 1	Visit 2	Visit 3	Visit 4	Visit 5
	Baseline	Week 2 (±1 d)	Week 8 (±3 d)	Week 12 (±3 d)	Week 16 (±5 d)
Informed consent/Photography Consent ^b	X				
Inclusion/Exclusion Criteria	X				
Demographics/ Relevant medical history/ Prior therapies ^c	X				
Urine Pregnancy test (UPT) ^d	X		X	X	X
Investigator's Global Assessment (IGA)	X	X	X	X	X
Global Assessment of Improvement				X	X ^a
PIH evaluation ^e	X	X	X	X	X
Local tolerance assessment	X	X	X	X	X
Photographs ^b	X ^h	X	X	X	X
Concomitant therapies	X	X	X	X	X
Adverse events ^f	X	X	X	X	X
Dispensation of investigational products	X		X		
Dispensation of non-investigational products	X		X		
Return of investigational products			X		X
Subject Diary/Compliance ^g		X	X	X	X
DLQI-cDLQI questionnaire	X			X	X ^a
Subject satisfaction questionnaire				X	X ^a
Cosmetic acceptability questionnaire					X ^a
Exit form					X ^a

- To be performed at Week 16 or before in case of early termination.
- Photography consent and standardized photography (mandatory criteria for inclusion in the trial).
- Only prior therapies that were stopped within 6 months of the baseline visit and that may have an impact on inclusion/exclusion criteria should be recorded. Treatment that continues after baseline should be recorded on the Concomitant Treatment Form of the CRF.
- UPT will have sensitivity down to at least 25 IU/L for hCG. UPT is mandatory at baseline, week 8, week 12 and week 16/early termination in female subjects
- If PIH present at baseline visit.
- Adverse event onsets after subject signature of the informed consent form should be recorded on the AE Form of the CRF.
- Subject diary is a diary which will be given to the subject to report the treatment application
- Sponsor Medical Expert will review the clinical evaluation of acne and give his confirmation for inclusion of subjects into the trial.

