Clinical trial title: Subject Reported Outcome with use of Adapalene 0.3% - benzoyl peroxide 2.5% in moderate to severe acne in Dark Skin Phototype subjects		
Short title (± acronym): Subject Reported Outcome in Dark Skin Phototype subjects with acne		
Project number: 816	Clinical trial phase: IV	Clinical trial period Q1 2017 – Q4 2017
Non-investigational product to be provided for the clinical trial:	
Cetaphil® DermaControl™ Oil control Foam Wash twice daily in the morning and in the evening)
 
Cetaphil® DermaControl™ Oil control Moisturizer SPF 30 once daily in the morning after washing (using Cetaphil® DermaControl™ Oil control Foam Wash) and to re-apply if sun exposure during the day.
 
Both products are topical and will be used on the whole face for 16 weeks
	
Measurement criteria	
Subject-reported outcomes
 
 • Dermatology Life Quality Index questionnaire (DLQI) or Children’s Dermatology Life Quality Index (cDLQI) questionnaires at Baseline, Week 12 and at Week 16/Early termination • Subject satisfaction questionnaire at Week 12 and Week 16/Early termination 
Efficacy
 
 • Investigator’s Global Assessment (IGA): acne severity of the face on a scale from 0 (Clear) to 4 (Severe) at each visit • Investigator’s Global Assessment of Improvement from baseline (GAI): improvement compared with baseline on a scale from 0 (Excellent improvement) to 5 (Worse) at Week 12 and Week 16/Early termination 
Safety
 
 • Post-inflammatory hyper-pigmentation (PIH) severity at each visit (if present at Baseline) • Local tolerance (erythema, scaling, dryness, stinging/ burning): severity score on a scale from 0 (None) to 3 (Severe) at each trial visit • Adverse Events throughout the trial 
Other
 
 • Photographs (visible light photos) at each visit • Cosmetic acceptability questionnaire regarding the non-investigational products, at Week 16/Early termination 	

Clinical trial title: Subject Reported Outcome with use of Adapalene 0.3% - benzoyl peroxide 2.5% in moderate to severe acne in Dark Skin Phototype subjects		
Short title (± acronym): Subject Reported Outcome in Dark Skin Phototype subjects with acne		
Project number: 816	Clinical trial phase: IV	Clinical trial period Q1 2017 – Q4 2017

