Analysed variables	Subject-reported outcomes 
 • DLQI/cDLQI at Baseline and at each evaluation time • Subject satisfaction questionnaire at each evaluation time Efficacy variable 
 • IGA score: % of subjects across scores at each visit • GAI score: % of subjects across scores at Week 12 and last visit Safety variables 
 • PIH severity: Raw value at each visit and % change from baseline at each post-baseline visit • Local tolerance: Raw value at each visit and worst-score across visit, % of Subjects across scores at each post-baseline visit • Incidence of adverse events Other 
 • Cosmetic acceptability questionnaire at Week 16/Early termination 	
Principal statistical methods and sample size calculation:	
The Intent-to-Treat (ITT) population consists of all enrolled subjects. The safety population (APT) consists of the ITT population, after exclusion of subjects who never took the treatment. Population definitions will be decided before the database lock.
 
The objective of this trial is to evaluate the subject reported outcome with Adapalene 0.3% - BPO 2.5% gel during 16 weeks of treatment.
 
No inferential statistics will be performed. All variables will be descriptively summarized on ITT population and on APT population for the safety variables. The last observation carried forward (LOCF) method will be used to impute missing efficacy values.
 
As no inferential statistics will be performed, no statistical rationale of sample size can be used. However, the subject reported outcomes (quality of life and satisfaction survey), can be evaluated with a total of 60 subjects.
	

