4.4. EXCLUSION CRITERIA

Any subject who meets at least one of the following criteria will not be eligible for the trial.

1. Subject with severe acne (IGA > 3) with more than 2 nodules, cysts, or extra-facial lesions,
2. Subject with acne conglobata, acne fulminans, secondary acne (chloracne, drug-induced acne, etc.), nodulo cystic acne, acne requiring systemic treatment,
3. Subject with history of lupus, atopic dermatitis, perioral dermatitis, dermatomyositis, rosacea on the face
4. Prior failure to treatment with Epiduo[®] Forte/TactuPump[™] Forte gel (Adapalene 0.3% - BPO 2.5%),

5. Subject with damaged facial skin (e.g. tattoo, cuts, skin abrasion , eczema or sunburned skin),
6. Subjects with skin phototype < IV,
7. Female subject who is pregnant, lactating or planning a pregnancy during the trial,
8. Female Taking Diane-35 or who is planning to change her contraceptive method or hormone replacement therapy during the trial,
9. Subject with known impaired hepatic or renal functions,
10. Subject with a wash-out period for **topical treatment** or procedures on the face less than:

Topical treatments: Corticosteroids, antibiotics, benzoyl peroxide, azelaic acid, dapson, hydroxyacids, Zinc containing treatments, , antiseptics, other anti-inflammatory products or other acne treatments (for example salicylic acid treatments/ transdermal contraceptives are forbidden if used to treat acne)	2 weeks
Retinoids	4 weeks
Cosmetic/aesthetic procedures on the face (e.g., comedone extraction, desquamating, or abrasive agents, adhesive cleansing strips)	1 week
Wax epilation	2 weeks
Photodynamic therapy	6 weeks
Laser therapy, microdermabrasion, deep chemical peel, plastic surgery for acne	3 months

11. Subject with a wash-out period for **systemic treatment** less than:

• Corticosteroids, (except locally acting corticosteroids such as inhaled or intrathecal or dermal application at distance from the face), tetracyclines, other antibiotics (except penicillin)	1 month
• Oral retinoids/isotretinoin/ anti-androgens / Cyproterone acetate / Chlormadinone acetate	6 months
• Spironolactone/ Drospirenone (except if at a stable dose for at least 3 months for drospirenone)	3 months
• Immunomodulators	3 months
• Oral contraceptives/ oral dapson for acne	1 month

12. Subjects with severe PIH (Score > 3 on PIH scale),
13. Subject with active or chronic skin allergies,

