5.5. CLINICAL TRIAL VISIT DESCRIPTION AND PROCEDURES

5.5.1. Visit 1 – Baseline visit

1. Explain the nature and the constraints of the clinical trial to the subject and to his/her parent(s) or guardian if the subject is under the age of 18,
2. If a female subject of childbearing potential agrees to participate to the clinical trial, make sure she is using the required method(s) of contraception,
3. Ensure the subject (and parent/guardian for subjects under the age of 18) has read, understood, dated and signed the approved Informed Consent Form (ICF),
4. Give a dated and signed copy of the ICF to each subject and parent/guardian if applicable,
5. Question the subject about demography (birthdate, race, skin phototype, gender), relevant medical history, prior therapies (stopped within 6 months of the baseline visit and that may have an impact on the inclusion/exclusion criteria) and concomitant therapies,
6. Inform subject about authorized and prohibited concomitant therapies,
7. Check inclusion/exclusion criteria (see sections 4.3 and 4.4),
8. Log into the IVR/IWR System to check the inclusion rate in terms of balance in ethnic/race background and acne severity,
9. Conduct a urine pregnancy test (UPT) for female subjects of childbearing potential,
10. Log into the eCRF to get a Subject Identification Number (SIN),
11. Perform an Investigator's Global Assessment (IGA) of the whole face (see section 7.2.1),
12. Assess the Post-Inflammatory Hyperpigmentation (PIH) severity if any (see section 7.3.1),
13. Perform the baseline Local Tolerability Assessment (erythema, scaling dryness and stinging/burning; see section),
Note: *Stinging/burning at the baseline visit should **NOT** be assessed at baseline,*
14. Take photographs of the face according to the provided procedure (subject and parent/guardian should accept through the approved ICF),
15. Question the subject about the occurrence of any adverse events (AEs) by asking an open ended question taking care not to influence the subject's answer, such as: "have you had any new symptoms, injuries, illness or side-effects or worsening of pre-existing conditions?" Record all events as appropriate on the corresponding AE eCRF pages,
16. If the subject is eligible, assign a kit number (see specific section 0) (to be reported on the prescription form),
17. Fill in a prescription form with the Subject's Identification Number,
18. The Product Dispenser (person in charge of products dispensation) will:

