5.5.2. Visit 2 (week 2) (\pm 1 Day)

1. Question the subject about occurrence of adverse events (AEs) and record occurrence of any events and/or any changes in events that were ongoing at the previous clinical trial visit. Document all changes in the eCRF,
2. Enquire whether any concomitant therapies have been added, stopped, or changed since the subject's last visit. Document all changes in the eCRF,
3. Perform an Investigator's Global Assessment (IGA) of the whole face (see section 7.2.1).
4. Assess the Post-Inflammatory Hyperpigmentation (PIH) severity if present at baseline (see section 7.3.1),
5. Perform Local Tolerability Assessment (erythema, scaling dryness and stinging/burning; see Section 7.3.2),
6. Take photographs of the face according to the provided procedure,
7. The Product Dispenser will:
 - a. Check the returned subject's diary and interview the subject about compliance (number of missed trial product applications),

- b. Emphasize again the importance of complying with the given instructions and treatments; instruct the subject to bring back the dispensed investigational product together with the subject's diary at the next visit,
 - c. For all female subjects, emphasize the guidelines about contraception and risks in case of pregnancy,
8. Schedule the next follow up visit, visit 3 (week 8) 8 weeks after Baseline visit \pm 3 days.

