5.5.5. Visit 5 (week 16) (±5 Days)

1. Question the subject about occurrence of adverse events (AEs) and record occurrence of any events and/or any changes in events that were ongoing at the previous clinical trial visit. Document all changes in the eCRF,
2. Enquire whether any concomitant therapies have been added, stopped, or changed since the subject's last visit. Document all changes in the eCRF,
3. Conduct a urine pregnancy test (UPT) for female subjects of childbearing potential.
4. Perform an Investigator's Global Assessment (IGA) of the whole face (see section 7.2.1),
5. Evaluate Global Assessment of Improvement of acne **versus baseline** (see section 7.2.2),

6. Assess the Post-Inflammatory Hyperpigmentation (PIH) if present at baseline (see section 7.3.1),
7. Perform Local Tolerability Assessment (erythema, scaling dryness and stinging/burning; see Section 7.3.2),
8. Take photographs of the face according to the provided procedure,
9. The Product Dispenser will:
 - a. Check the returned investigational product, the subject's diary and interview the subject about compliance (number of missed trial Products applications),
 - b. Ensure that the subject has returned all used/unused investigational products and the subject Diary. All missing investigational product units must be documented in the Product Dispensation Log comments section and on other accountability form.
 - c. For all female subjects, reiterate the guidelines about contraception and risks in case of pregnancy during 1 month after the end of the trial.
10. Ask the subject to complete the week 16/end of the trial DLQI/cDLQI questionnaire,
11. Ask the subject to complete Subject Satisfaction and Cosmetic acceptability questionnaires,
12. Complete the Exit Form in the eCRF and give the reason for clinical trial discontinuation (see section 4.5.6).

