7.3. SAFETY ASSESSMENTS

Safety assessments will be conducted for all subjects at the baseline visit (after the ICF has been signed) and every subsequent visit. The safety parameters include adverse events (AEs) and increase in Post inflammatory hyperpigmentation (PIH) and local tolerance severity.

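### The protocol disagrees with itself on who is scored for PIH after baseline, and its only PIH change variable, % change on a 0-4 grade, is undefined at 0 and can give a mean with the wrong sign

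*Combined protocol and SAP*

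**What the plan says.** **Restrictive text.** The PIH row of the flow chart in 5.4 carries the footnote "If PIH present at baseline visit". The synopsis (measurement criteria, safety) attaches the same condition. So do the visit procedures: 5.5.2 reads "Assess the Post-Inflammatory Hyperpigmentation (PIH) severity if present at baseline", 5.5.3 and 5.5.4 repeat it, and 5.5.5 has "Assess the Post-Inflammatory Hyperpigmentation (PIH) if present at baseline". At baseline, 5.5.1 says "Assess the Post-Inflammatory Hyperpigmentation (PIH) severity if any", which leaves open whether a zero is recorded.

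**Unconditional text.** Section 7.3 says "Safety assessments will be conducted for all subjects at the baseline visit (after the ICF has been signed) and every subsequent visit" and names an increase in PIH as a safety parameter. Section 7.3.1 has PIH evaluated at each visit on a scale where 0 is none and 4 is severe, and makes any rise in score an adverse event. Section 7.5 repeats the each-visit evaluation. None of the three mentions a baseline condition. Exclusion criterion 12 (4.4) removes scores above 3 and sets no minimum, so subjects at grade 0 are eligible.

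**Analysis.** The synopsis plans "PIH severity: Raw value at each visit and % change from baseline at each post-baseline visit", and 9.1.1 says the same. No absolute change, shift table, new-onset count or rule for a baseline of 0 is given. Section 9.1.3 gives ordinal data both frequencies and the usual statistics, including mean and median. Section 9.1.2.3 leaves missing PIH values as observed.

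**The concern.** Sites following different sections would score different subjects. Under the restrictive text, a subject who starts at 0 and develops PIH on treatment has no scheduled score. The event reaches the tables only as an adverse event (7.3.2, 8.1.1, 9.1.3), with an adverse-event intensity but no 0-4 grade. If baseline zeros are recorded but not followed, the raw means and frequencies also change denominator after baseline.

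The change variable is a separate defect. A percentage of an ordinal grade has no value at 0 and weights the same one-grade step three times as heavily from grade 1 as from grade 3.

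This matters because the background (2.1) presents PIH as a feature that sets acne in skin of color apart, 7.3 makes its increase a safety parameter, and the hypothesis in 3.2 includes good tolerance.

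**Working it through.** The plan gives no figure to reproduce: 9.2 states that 60 subjects has no statistical rationale. Inputs from the documents are N = 60 (4.1), baseline grades 0 to 3 (4.4), post-baseline grades 0 to 4 (7.3.1) and four post-baseline visits (5.4). The share at baseline grade 0 (f) and the mean baseline grade of the other subjects (m) are not given and are assumed over a range.

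**1. The percentage scale.** % change = 100 × (post − baseline) / baseline.

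| Baseline | Post 0 | Post 1 | Post 2 | Post 3 | Post 4 |
|---|---|---|---|---|---|
| 0 | undefined | undefined | undefined | undefined | undefined |
| 1 | −100 | 0 | +100 | +200 | +300 |
| 2 | −100 | −50 | 0 | +50 | +100 |
| 3 | −100 | −66.7 | −33.3 | 0 | +33.3 |

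**2. Sign reversal.** Take 10 subjects going 1 to 2 and 15 going 3 to 2.
- Mean grade change = (10 − 15)/25 = −0.2, an improvement.
- Mean % change = (10 × 100 − 15 × 33.3)/25 = +20%, an apparent worsening.
- Median % change = −33.3%, not reversed.

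In general, let *a* subjects go 1 to 2 and *b* go 3 to 2. Mean grade change is negative when b > a, and mean % change is positive when 100a > 33.3b, that is b < 3a. The mean therefore reverses for a < b < 3a. For 2 to 1 against 1 to 2, the window is a < b < 2a.

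**3. How likely is reversal?** A simulation with N = 60 and 3,000 runs per scenario assumed 20%, 25%, 30% and 25% of subjects at baseline grades 0, 1, 2 and 3. The mean reversed in about 22% of runs when low grades tended to worsen while high grades improved, about 1% under uniform modest improvement, and 0% under strong improvement.

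**4. Subjects lost.** For f = 10%, 25% or 40%, 60 × f = 6, 15 or 24, leaving 54, 45 or 36. Under the restrictive text these are the subjects scored after baseline. If all subjects are scored, they are those with a defined % change.

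**5. Denominator artefact** (only if baseline zeros are recorded and then not followed). Suppose no subject changes. The baseline mean is m(1 − f) and later means are m, a spurious rise of f × m.
- At m = 2 the rise is 0.2, 0.5 or 0.8 grades.
- Over m = 1 to 3 it runs from 0.1 × 1 = 0.1 to 0.4 × 3 = 1.2.
- The share with any PIH moves from 90%, 75% or 60% at baseline to 100% after.
- At f = 25%, a real improvement from 2.0 to 1.5 in the scored subjects is displayed as 2.0 × 0.75 = 1.5 (n = 60) and then 1.5 (n = 45).

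**The case against.** The best defence is that the synopsis, flow chart and four visit lists all agree, and that the all-subjects wording in 7.3 is a general lead-in which already yields to specifics: stinging/burning is not assessed at baseline. That does not dispose of 7.3.1, which is the PIH-specific section the visit steps refer to. A move from 0 to 1 is a rise in score under its adverse-event rule, yet the restrictive text schedules no score to detect it.

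Several limits do stand.
- The two defects belong partly to opposite readings. If only subjects with PIH are followed, every scored subject has a baseline of 1 to 3 and % change is defined; only the unequal weighting remains.
- The denominator artefact needs zeros recorded at baseline. The printed number of values would show the drop, and within-subject % change is unaffected by it. The 1.2-grade extreme requires every other subject to be at grade 3.
- New-onset PIH may well be noticed: standardized facial photographs, IGA and local tolerance examinations take place at every visit. No PIH grading from photographs is planned, however, so what is lost is a scheduled score.
- Reversal of the mean is possible rather than expected, and the median is far less exposed. In the worked example, the 10 of 25 who worsened would also be adverse events.
- The separate SAP announced in 9.1 was not available and may handle baseline zeros. It cannot recover scores that sites were told not to take.

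**Conclusion.** The concern holds and should be fixed. The contradiction is in the text, and neither reading is satisfactory as written: the restrictive one leaves new-onset PIH ungraded, and the all-subjects one produces undefined % changes. The unequal weighting is present under both. Raw values and frequencies do not share the ratio problem, but they do not show within-subject change.

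The numbers of subjects affected and the size of the denominator artefact rest on assumed shares at grade 0 and assumed mean grades; the reversal frequencies rest on assumed grade distributions. The percentage table and the reversal windows are exact. PIH is one descriptive safety variable, no decision rule depends on it, and the main objective is subject-reported outcomes. The consequence is a safety description that may be incomplete or point the wrong way, not a threat to the main result.

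**What to change.** Make both changes together, because scoring everyone while keeping % change would only add undefined values.

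1. **Assessment.** Remove the baseline-presence condition from the synopsis, the 5.4 footnote and 5.5.2 to 5.5.5, and remove the equivalent qualifier in 5.5.1. A grade, including 0, is then recorded for every subject at every visit, in line with 7.3 and 7.3.1.
2. **Analysis.** In the synopsis and 9.1.1, replace % change with a baseline-by-visit shift table, absolute grade change, n (%) improved, unchanged and worsened, and n (%) with new-onset PIH among subjects at grade 0 at baseline. Keep the raw values and frequency distributions.

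The cost is one five-point score at each of four post-baseline visits for subjects starting at 0: 4 × 6, 15 or 24 = 24, 60 or 96 scores under the assumed shares, taken during the facial examination already done for IGA. Beyond that it needs protocol wording, a small eCRF change and one table. Section 9.1 has the SAP finalized only before database lock, so the analysis part fits the existing timetable.
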